3. INVESTIGATIONAL PLAN

3.1. Study Design

This Phase II, randomised, double-blind, parallel group, placebo controlled, multicentre study of 52 weeks treatment duration will evaluate the efficacy, safety and tolerability of weekly albiglutide versus placebo when added to insulin therapy in subjects with

NOT1DM and residual insulin production. The primary endpoint is mean change from baseline in mixed meal stimulated 2 hour plasma C-peptide AUC at Week 52.

Subjects within 8 weeks of diagnosis, who are receiving insulin treatment or have received insulin at some time between the date of diagnosis and the first dose of study drug, with one or more positive T1DM associated auto-antibodies, and a stimulated peak C-peptide > 0.2 nmol/L, signifying clinically relevant residual C-peptide production (as a measure of β cell function), will be eligible to enter the study.

[figure not shown]
After screening, approximately 68 eligible subjects will be randomised in a 3:1 ratio such that:

- 51 subjects receive albiglutide 30 mg once weekly (with increase to 50 mg once weekly at Week 6 if the 30-mg weekly dose is tolerated) added-on to insulin therapy
- 17 subjects receive placebo once weekly added-on to insulin therapy

During the study, subjects will perform self monitoring of plasma glucose at least 4 times daily and adjust their basal and meal-time insulin requirements according to protocol-defined algorithm/guidance (See Section 5.1.2).

The total duration of a subject's participation will be approximately 72 weeks (up to 8 weeks of Screening, 52 weeks of treatment and 12 weeks of Post-treatment Follow-up) (Figure 1). Subjects will have 12 study centre visits and at least 14 telephone calls.

Figure 1 Study Schematic for GLP110933

Potential events of pancreatitis will be adjudicated by an independent pancreatitis adjudication committee (PAC).

Subject completion is defined as completion of all periods of the study up to and including the follow-up period.

There will be no compassionate use of study medication once a subject completes or withdraws early from the study.

Protocol waivers or exemptions are not allowed with the exception of immediate safety concerns. Therefore, adherence to the study design requirements, including those specified in the Time and Events Table ([Table 3](#)), are essential and required for study conduct.

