The half-life of albiglutide is approximately 5 days, and significant therapeutic concentrations can persist for up to 5 half-lives (3 to 4 weeks) after discontinuation. Therefore, the investigator should use caution when prescribing treatment after the withdrawal of active study medication taking into consideration the long half-life of albiglutide (see Section 5.6.2 for prohibited anti-diabetic medications for subjects discontinuing study medication early but still participating in the study), taking into consideration the long half-life of albiglutide.

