8.2. Safety Analyses

8.2.1. Overview of Planned Adverse Events Analyses

The safety analyses will be based on the “Safety” population, unless otherwise specified.

Table 6 provides an overview of the planned analyses, with further details of data displays being presented in [Appendix 13: List of Data Displays](#).

Table 6 Overview of Planned Adverse Event Analyses

Endpoint / Parameter/ Display Type	Absolute		
	Summary		Individual
	T	F	L
Adverse Events (AEs)			
Overview of AEs	Y		
All AEs by SOC and PT	Y [2]		Y
Common AEs by Overall Frequency	Y [3]		
Drug-Related AEs by SOC and PT	Y [2]		
All AEs by SOC and PT and Maximum Intensity	Y [2]		
Drug-Related AEs by SOC and PT and Maximum Intensity	Y [2]		
Common Non-Serious AEs by SOC and PT (Subjects & No. of Occurrences)	Y [3]		
Subject Numbers for Individual AEs			Y
Relationship Between AE SOCs, PT and Verbatim Text			Y
Serious and Other Significant AEs			
Serious AEs	Y [1]		
Reasons for Considering as a Serious AE			Y
Drug-Related Serious AEs [9]			
Serious AEs by SOC and PT (Subjects & No. of Occurrences)	Y [3]		
Fatal Serious AEs [9]			Y
Drug-Related Fatal Serious AEs [9]			
Non-Fatal Serious AEs [9]			Y
Drug-Related Non-Fatal Fatal Serious AEs [9]			
AEs Leading to Permanent Discontinuation of Study Treatment by SOC and PT	Y [3]		Y
AEs Leading to Withdrawal from Study by SOC and PT	Y [2]		Y
Other Significant AEs [7]			
AEs of Special Interest			
Overview of Adverse Events of Special Interest	Y [3]		
Investigator-Reported Cardiovascular Events by SOC and PT	Y [3]		Y
Investigator-Reported Atrial Fibrillation/Atrial Flutter by SOC and PT	Y [3]		Y
Subject-Reported Hypoglycaemic Events by ADA category in 3-monthly Intervals	Y [6]		
Subject-Reported Hypoglycaemic Events with plasma glucose <3.1 mmol/L	Y [6]		
Subject-Reported Daytime/Nocturnal Hypoglycaemic Events by ADA category	Y [6]		
Subject-Reported Hypoglycaemic Events over Time	Y [6]	Y [6]	
Subject-Reported Hypoglycaemic Events			Y
Investigator-Reported Pneumonia Events by SOC and PT	Y [3]		Y
Investigator-Reported Pancreatitis Events by SOC and PT	Y [3]		Y

Endpoint / Parameter/ Display Type	Absolute		
	Summary		Individual
	T	F	L
Positively Adjudicated Pancreatitis Events by SOC and PT	Y [3]		
Investigator-Reported Thyroid Adverse Events by SOC and PT	Y [3]		Y
Gastrointestinal (GI) Events by SOC and PT	Y [3]		
GI Events Over Time [4]	Y [3]		
Summary of Characteristics of Events [5]	Y [3]		

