Investigator-Reported Investigational Product Injection Site Reactions by SOC and PT	Y [3]		Y
Summary Characteristics of Investigator-Reported Investigational Product Injection Site Reactions	Y [3]		
Summary Characteristics of Investigator-Reported Investigational Product Injection Site Reactions by Anti-Albiglutide Antibody Status	Y [3]		
Investigator-Reported Systemic Allergic Reactions	Y [3]		Y
Liver Monitoring/Stopping Event Reporting	Y [8]		Y
Liver Events (Customised MedDRA Query) by SOC and PT	Y [3]		Y
Investigator-Reported Renal Impairment by SOC and PT	Y [3]		Y
Diabetic Ketoacidosis (DKA) by SOC and PT	Y [3]		Y
Appendicitis by SOC and PT	Y [3]		Y
Pancreatic Cancer by SOC and PT	Y [3]		Y
Malignant Neoplasms by SOC and PT	Y [3]		Y

NOTES:

- T = Table, F = Figures, L = Listings, Y = Yes display generated, SOC = System Organ Class, PT = Preferred Term.
- Summary = Represents TF related to any summaries (i.e. descriptive statistics) of the observed raw data.
- Individual = Represents FL related to any displays of individual subject observed raw data.
- [1] Produced for the pre-therapy, on-therapy and post-therapy phases separately.
- [2] Produced for the on-therapy and post-therapy phases separately.
- [3] Produced for the on-therapy phase only.
- [4] Produced for any GI event
- [5] Produced for Diarrhoea, Nausea, and Vomiting
- [6] Includes all events, on-therapy and post-therapy combined.
- [7] There are no other significant adverse events identified in this study; however AEs of special interest have been defined.
- [8] Combined on-therapy and post-therapy summary table.
- [9] Due to the low number of serious AEs reported, summary tables will not be produced for these events.

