8.2.1.7.1. Cardiovascular Events

Investigators will be required to fill out event specific data collection tools for the following AEs and SAEs:

- Myocardial infarction/unstable angina
- Congestive heart failure
- Arrhythmias including atrial fibrillation/flutter
- Valvulopathy
- Pulmonary hypertension
- Cerebrovascular events/stroke and transient ischemic attack
- Peripheral arterial thromboembolism
- Deep venous thrombosis/pulmonary embolism
- Revascularisation

Cardiovascular events are reported by the Investigator on specific eCRFs for each event. These events are not adjudicated.

8.2.1.7.2. *Atrial Fibrillation/Atrial Flutter*

In addition to being included within the cardiovascular event ‘arrhythmias’ above, atrial fibrillation/atrial flutter events are also reported by the Investigator on a specific atrial fibrillation/atrial flutter eCRF.

8.2.1.7.3. *Subject-Reported Hypoglycaemic Events*

Subject-reported hypoglycaemia summaries include on-therapy and post-therapy events.

Hypoglycaemic events are reported in a subject eDiary; any meeting the SAE criteria are also reported in the adverse event data. The following summaries use subject-reported data (see Section 11.5.3). Incidence will be reported using the number and percentage of subjects experiencing events and the number of events.

Incidence of hypoglycaemia (in total and by each category as defined by ADA criteria) overall and in 3 monthly intervals will be summarised by treatment group.

Incidence of daytime hypoglycaemia (in total and by ADA category) and nocturnal hypoglycaemia (in total and by ADA category) will be summarised by treatment.

Incidence of hypoglycaemia with plasma glucose <3.1 mmol/L (< 56mg/dL), regardless of symptoms, will be summarised by treatment.

The number and percentage of subjects reporting hypoglycaemia during each two week period will be presented by treatment group. A summary table and plot will be produced. In addition, the number of hypoglycaemic events reported per subject during each two week period will be presented by treatment group. A summary table will be produced, and the mean number of hypoglycaemic events reported per subject during each two week period will be plotted.

Further exploratory analysis may be done, depending on the amount of missing data.

A by-subject listing of all subject-reported hypoglycaemic events will be produced.

Note: subject-reported hypoglycaemic events are also summarised as part of the secondary efficacy endpoints.

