ADA classification	Required Assistance	Symptoms	Glucose Reading (mmol/L)
Severe	Yes	Any*	Any*
Documented Symptomatic	No or missing	Yes	$0 < \text{glucose} \leq 3.9$
Asymptomatic	No or missing	No or missing	$0 < \text{glucose} \leq 3.9$
Probable Symptomatic	No or missing	Yes	Glucose = 0 or missing
Pseudo	No or missing	Yes	Glucose > 3.9

* includes missing values

- A subject reported event that does not meet any of the above criteria will not be counted as a hypoglycaemic event (any events will be flagged to the study team for review).
- Only hypoglycaemic events that subjects record in the glucose meter will be included in the summaries of subject-reported hypoglycaemic events. Glucose readings reported, for example, as part of standard laboratory testing or the 7-point glucose profile will not be included.
- Each event will be assigned to one ADA category, but a subject may report events from multiple ADA categories. A subject will appear in all ADA categories they experience.

Daytime/Nocturnal Events

- Subjects report the start date/time of a hypoglycaemia event. The start time of event will be used to classify the event as daytime or nocturnal.
- Daytime Hypoglycaemia: an event with an onset time between 06:00h and 00:00h (inclusive). i.e., in SAS time format (secs): start time = 0 or start time > 21541
- Nocturnal Hypoglycaemia: an event with an onset time between 00:01h and 05:59h (inclusive). i.e., in SAS time format (secs): $0 < \text{start time} \leq 21540$
- Events with a missing start time will be classified as Daytime events

Time periods (3 monthly intervals)

 Events will be assigned to time periods will are defined using the following categories: Baseline to \leqWeek 12: Study day 1 to \leq84 $>$Week 12 to \leqWeek 24: Study day 85 to \leq168 $>$Week 24 to \leqWeek 36: Study day 169 to \leq252 $>$Week 36 to \leqWeek 52: Study day 253 to \leq364 $>$Week 52 to \leqWeek 64: Study day 365 to \leq448
Time periods (2 weekly intervals)

 A summary of events by 2 weekly time periods will also be produced. E.g., Day 1 to Day 14; Day 15 to Day 28; etc.
Denominators for time period summaries

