3.18.	Safety	AE1	Summary of Post-therapy Adverse Events Leading to Withdrawal from Study by System Organ Class and Preferred Term		SAC [1]
Adverse Events of Special Interest					
3.19.	Safety	GLP113121, Switch	Overview of On-therapy Adverse Events of Special Interest		SAC [1]
3.20.	Safety	AE1	Summary of On-therapy Investigator-Reported Cardiovascular Events by SOC and PT		SAC [1]

Safety : Tables					
No.	Population	IDSL / TST ID / Example Shell	Title	Programming Notes	Deliverable [Priority]
3.21.	Safety	AE1	Summary of On-therapy Investigator-Reported Atrial Fibrillation / Atrial Flutter by SOC and PT		SAC [1]
3.22.	Safety	New template needed, see DEFEND-1	Summary of Subject-Reported Hypoglycaemic Events by Time Period (3-monthly intervals) and ADA Category		SAC [1]
3.23.	Safety	Switch	Summary of Subject-Reported Hypoglycaemic Events by Plasma Glucose Level		SAC [1]
3.24.	Safety	Switch	Summary of Subject-Reported Daytime and Nocturnal Hypoglycaemic Events by ADA Category		SAC [1]
3.25.	Safety	New	Summary of Subject-Reported Hypoglycaemic Events over Time (2-weekly intervals)	2-weekly intervals	SAC [1]
3.26.	Safety	AE1	Summary of On-therapy Investigator-Reported Pneumonia by SOC and PT		SAC [1]
3.27.	Safety		Summary of On-therapy Investigator-Reported Pancreatitis by SOC and PT		SAC [1]
3.28.	Safety		Summary of On-therapy Investigator-Reported Pancreatitis (Positively Adjudicated by the PAC) by SOC and PT		SAC [1]
3.29.	Safety		Summary of On-therapy Pancreatic Cancer identified from a Customised MedDRA Query by SOC and PT		SAC [1]
3.30.	Safety	AE1	Summary of On-therapy Investigator-Reported Thyroid Events by SOC and PT		SAC [1]
3.31.	Safety	AE1	Summary of On-therapy Gastrointestinal Events by SOC and PT		SAC [1]
3.32.	Safety	GLP113121, Switch	Summary of On-therapy Gastrointestinal Events Over Time		SAC [1]
3.33.	Safety	GLP113121	Summary Characteristics of On-therapy Diarrhoea		SAC [1]

Safety : Tables					
No.	Population	IDSL / TST ID / Example Shell	Title	Programming Notes	Deliverable [Priority]
3.34.	Safety	GLP113121	Summary Characteristics of On-therapy Nausea		SAC [1]
3.35.	Safety	GLP113121	Summary Characteristics of On-therapy Vomiting		SAC [1]
3.36.	Safety	AE1	Summary of On-therapy Investigator-Reported Injection Site Reactions by SOC and PT		SAC [1]
3.37.	Safety	GLP113121, Switch	Summary Characteristics of On-therapy Investigator-Reported Injection Site Reactions		SAC [1]

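### Tables 3.23 and 3.24 mix the 52-week treatment period with the 12-week off-treatment follow-up for hypoglycaemia below 3.1 mmol/L and daytime/nocturnal hypoglycaemia

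*SAP*

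**What the plan says.** In SAP 8.2.1, Table 6, the rows "Subject-Reported Hypoglycaemic Events with plasma glucose <3.1 mmol/L" and "Subject-Reported Daytime/Nocturnal Hypoglycaemic Events by ADA category" both carry note [6]: "6] Includes all events, on-therapy and post-therapy combined". SAP 8.2.1.7.3 repeats the rule: "Subject-reported hypoglycaemia summaries include on-therapy and post-therapy events". SAP 11.5.3 says the same where it describes how these events are reported.

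In the list of displays (SAP 11.13.7), Table 3.23 summarises events by plasma glucose level and Table 3.24 is the "Summary of Subject-Reported Daytime and Nocturnal Hypoglycaemic Events by ADA Category". Neither title names a phase or interval. The two sibling tables under the same note are split by time: Table 3.22 by 3-monthly intervals, with a separate one from after Week 52 to Week 64, and Table 3.25 by two-week periods. SAP 8.2.1.7.3 reports incidence as the number and percentage of subjects with events and the number of events.

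Four other statements bear on this:

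- Protocol 3.1 gives the schedule as "52 weeks of treatment and 12 weeks of Post-treatment Follow-up". SAP 11.5.3 places the last interval at Study Days 365 to 448.
- SAP 11.3.2.2 counts a hypoglycaemic event as on-therapy up to 56 days after the last dose.
- SAP 8.2.1.7 says that summary tables for adverse events of special interest (AESI) present on-therapy events.
- Protocol 4.4 says of albiglutide that "significant therapeutic concentrations can persist for up to 5 half-lives (3 to 4 weeks") after it is stopped.

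**The concern.** Both endpoints are protocol safety endpoints (Protocol 6.4.1), and these tables are their only planned summaries. Hypoglycaemia in combination with insulin is listed as an identified risk (Protocol 1.3.1), and this is the first albiglutide study in this indication (Protocol 1.3).

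A reader of Tables 3.23 and 3.24 wants to know whether adding albiglutide to insulin changes clinically important or nocturnal hypoglycaemia. The pooled figure answers a different question, because it adds twelve weeks in which neither arm is scheduled to take study drug while insulin titration continues. With about 17 placebo subjects, even a modest shift could change how the descriptive comparison reads.

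The SAP also gives two rules for the same kind of table. SAP 8.2.1.7 says on-therapy; note [6] and 8.2.1.7.3 say on-therapy and post-therapy together.

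**Working it through.** The documents give no hypoglycaemia rates and no planned figure for these endpoints, so there is nothing of the plan's own to reproduce beyond the length of follow-up. Rates and rate ratios (RR) below are assumptions.

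**1. Share of time off treatment.** Days 365 to 448 are 448 − 365 + 1 = 84 days, or 12 weeks, as the protocol states. For a completer with last dose at Day 364 the share is 84/448 = 18.75%.

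**2. What post-therapy means in note [6].** On-therapy runs to last dose + 56 days, so to Day 364 + 56 = 420. Post-therapy is then 448 − 420 = 28 days, or 28/448 = 6.25%. With last dose at Day 358 it is 448 − 414 = 34 days, or 7.6%. The SAP's on-therapy state therefore keeps about 8 of the 12 off-treatment weeks.

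**3. Effect on a rate ratio.** With a constant placebo rate and equal follow-up in both arms:

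pooled RR = (RR_on × T_on + RR_off × T_off) / (T_on + T_off)

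| Assumption | Calculation | Pooled RR |
|---|---|---|
| RR_on 1.5, RR_off 1, effect ends at Week 52 | (52 × 1.5 + 12)/64 | 1.41 |
| RR_on 1.5, RR_off 1, effect lasts 4 more weeks | (56 × 1.5 + 8)/64 | 1.44 |
| RR_on 2, RR_off 1, effect ends at Week 52 | (52 × 2 + 12)/64 | 1.81 |
| RR_on 0.5, RR_off 1, effect ends at Week 52 | (52 × 0.5 + 12)/64 | 0.59 |
| RR_on 2, RR_off 2 | (52 × 2 + 12 × 2)/64 | 2.00 |
| RR_on 2, RR_off 3 | (52 × 2 + 12 × 3)/64 | 2.19 |
| RR_on 2, RR_off 0.5 | (52 × 2 + 12 × 0.5)/64 | 1.72 |

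Restricting instead to the SAP's on-therapy state, with RR_on 1.5 and RR_off 1 from Day 365, gives (364 × 1.5 + 56)/420 = 1.43. That is hardly different from the pooled 1.41.

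**4. Effect on the percentage of subjects affected.** This is closer to what the tables will show. Use 1 − exp(−rate × time), a placebo rate of 1 event per year, RR_on 2 and RR_off 1.

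- To Day 364: placebo 63.1%, albiglutide 86.4%, difference 23.3 points.
- To Day 448: placebo 70.7%, albiglutide 89.2%, difference 18.5 points.
- At 3 events per year the difference goes from 4.8 to 2.4 points.

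Part of each fall is saturation from longer observation, not dilution alone.

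**5. Early discontinuation.** Subjects who stop study drug are asked to keep completing hypoglycaemia diaries and attending the meal-test visits through to Week 64 (Protocol 4.4). For one who stops at Day 112, (448 − 112)/448 = 75% of the time to Week 64 is off drug. Cutting at Day 364 still leaves (364 − 112)/364 = 69% of the remaining time off drug.

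**The case against.** The strongest reply is that these are descriptive tables that follow the protocol. The two endpoints carry no time limit in Protocol 6.4.1, hypoglycaemia is collected to the follow-up contact, and Protocol 8.3.5.4 rules out inferential testing of safety variables. Every event is listed by subject, and AESI listings are to flag the therapy phase. All of this stands, and it limits the consequence. It does not make the pooled figure a treatment-period comparison, and it leaves the reader to retabulate from listings.

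Several stronger readings are tempting, but the documents do not support them:

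- A reader might take post-therapy in note [6] to be the whole 12-week follow-up. By SAP 11.3.2.2 it is only about the last 4 weeks in completers.
- A reader might infer that the protocol says the drug effect is gone after 3 to 4 weeks. Protocol 4.4 speaks of concentrations that can persist for up to that long. Protocol 3.2 treats an effect on insulin secretion at Week 64 as an open question.
- A reader might conclude that pooling must dilute any albiglutide effect. That requires a weaker effect off drug than on drug. If the effects are equal nothing changes, and if the off-drug ratio is larger the pooled ratio rises.
- A reader might think these are the only AESI tables not limited to on-therapy events. The liver monitoring/stopping table is also combined (note [8]).
- A reader might think that only Tables 3.22 and 3.25 separate out the follow-up. Tables 2.21 and 2.22 stop at Week 52, but they cover events at or below 3.9 mmol/L and/or needing third-party help, with no split at 3.1 mmol/L or by time of day.

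**Conclusion.** The point holds in a limited form. Tables 3.23 and 3.24 mix treatment and off-treatment time with no period breakdown, and the SAP's general rule for AESI tables disagrees with its rule for these two.

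The size is modest in completers: 18.75% of observation time, and at most that share of the excess or deficit in event rate if the off-drug ratio is 1. The figures of 1.41 to 1.44 for a true 1.50 rest on that assumption, a constant placebo rate and full follow-up. They illustrate the mechanism and do not predict what the tables will show, since no rate ratio is planned. The mixing can be much larger in subjects who stop drug early and stay in the study. No test, power calculation or primary conclusion is affected.

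**What to change.** Present Tables 3.23 and 3.24 by period, using the Week 52 boundary in SAP 11.5.3: Study Day 1 to 364 as the main column and Day 365 to 448 as a separate column. The total to Week 64 may be kept as a third. Apply the at-risk denominators that SAP 11.5.3 already sets for time-period summaries.

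Because a calendar cut leaves early discontinuers' off-drug time in the main column, also flag or show events and person-time on study drug. Switching the tables to the SAP's on-therapy state is not a substitute: it would remove only about 4 weeks in completers.

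Amend note [6], SAP 8.2.1.7.3 and SAP 11.5.3 together, and reconcile them with SAP 8.2.1.7. Changing the note alone would leave the same rule standing in the other two places. Table 3.22 already shows the follow-up interval separately and needs no change.

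The cost is one or two extra columns in two descriptive tables, plus the on-drug flag. No new data are needed.

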8.2.1.1. Adverse Events

Adverse events will be categorized by their occurrence in regard to therapeutic phase (pre-therapy, on-therapy, or post-therapy) as defined in Section 11.3.2.1.

All AEs will be coded using MedDRA, with MedDRA version updates throughout the study when available. In general, AEs will be presented in descending order starting with the system organ class (SOC) with the highest total incidence (that is, summed across all treatment groups) for any adverse event within the class, to the SOC with the lowest total incidence. Within each SOC level, AEs will be presented in descending order from the MedDRA preferred term (PT) with the highest total incidence to the PT with the lowest

total incidence. If the total incidence for any two or more PTs within an SOC is equal, the PTs will be presented in alphabetical order. A PT will not be presented if no adverse events occur within the level.

Only hypoglycaemic events which met the definition of an SAE were to be reported as adverse events. Any hypoglycaemic events reported as an AE will be included in the adverse event summary tables. Hypoglycaemic events will be reported separately (see Section 8.2.1.7.3).

An overview summary of the number and percentage of subjects with any AE, the total number of AEs recorded, and the overall AE density for on-therapy AEs (defined in Section 11.5.3) will be provided by treatment group. The overview will also summarise SAEs (including fatal, non-fatal and drug-related), drug-related AEs, AEs leading to discontinuation of study treatment and/or withdrawal from the study, AEs by maximum intensity, and AEs by therapy phase. This summary will include all AEs from the pre-therapy, on-therapy and post-therapy phases. The summary table will indicate if the drug-related AEs are related to blinded study medication (albiglutide/placebo) or insulin.

If any AE summary table does not contain any adverse events, then the summary table will be produced with a statement indicating that there are no adverse events to report.

